5 EFFICACY AND SAFETY VARIABLES

5.1 Adverse Events (see Section 6)

For subjects who are experiencing ongoing unresolved and possibly related TEAEs at the time of study completion or early discontinuation from the study, it will be recommended that the investigator schedule an appropriate follow-up visit in order to determine the event outcome. If the outcome of the related TEAE cannot be determined during the follow-up visit, the investigator will make reasonable attempts to contact the subject via telephone, post, or certified mail for up to 30 days after study completion or early discontinuation from the study to assess the outcome of the event. Any additional data will be documented and made available to the sponsor. The sponsor medical monitor will determine when the data needs to be documented on the CRFs.

5.2 Ocular Safety Assessments

All ocular safety evaluations will be performed on both subject eyes at baseline (pre-dose on Day 1) and after the study drug removal on Days 8 ± 1 and 15 ± 1 .

Intraocular pressure measurement (Goldmann applanation tonometry) should be done after the evaluations on chalazion and photography of chalazion and slit-lamp biomicroscopy evaluation are completed. All IOP pressure will be recorded in mmHg. To avoid IOP changes due to the diurnal rhythm, the IOP measurements should be performed at approximately the same time of the day on Days 1, 8 ± 1 , and 15 ± 1 . For subjects aged ≤ 12 years who have difficulty with Goldmann, Tono-Pen or iCARE may be used to measure IOP throughout the study. The same instrument should be used for measurement of the IOP for the study for each subject.

Visual acuity evaluation will be performed at all study visits with Snellen eye chart at 20 feet (6 meters). If the corrected or uncorrected VA is 20/40 or better, no additional refraction is necessary. If corrected or uncorrected VA is worse than 20/40, then an updated refraction must be performed. This refraction must be used for all VA assessments during the study. The subject must wear the same glasses, if applicable, at each visit. For subjects with surgical monovision correction, VA assessment may be conducted in the near vision eye with a near vision reading card held at approximately 14 inches from the subject's eye.

5.3 Skin Irritation Assessment (TDS Related Skin Irritation)

The investigator will assess skin irritation of the site application area for the TDS separate from the area affected by the study chalazion (i.e., excluding the chalazion itself) on the study eyelid. This skin assessment of the surrounding area will be conducted at baseline (pre-dose on Day 1) and after the study drug removal on Days 8 ± 1 and 15 ± 1 . On Days 8 ± 1 and 15 ± 1 , assessments will be conducted approximately 30 minutes to 1 hour after study drug removal in the clinic. This evaluation should be done by the same investigator throughout the study period as much as possible.

Table 2: Dermal Response Scale (Draize)

Score	Score Description
0	No evidence of erythema
1	Very slight erythema
2	Well defined erythema
3	Moderate to severe erythema
4	Severe erythema (beet redness) to slight eschar formation (injuries in depth)

5.4 Patch Adhesion Evaluation

The patch adhesion will be evaluated by the investigator using the following 5-point scale prior to patch removal on Days 8 ± 1 and 15 ± 1 in the study eyelid only. This evaluation should be done by the same investigator throughout the study period as much as possible.

- 0 = $\geq 90\%$ adhered (essentially no lift off of the skin)
- 1 = $\geq 75\%$ to $< 90\%$ adhered (some edges only lifting off the skin)
- 2 = $\geq 50\%$ to $< 75\%$ adhered (less than half the system lifting off the skin)
- 3 = $< 50\%$ adhered (more than half the system lifting off the skin without falling off)
- 4 = patch detached (patch completely off the skin)

5.5 Ocular and Skin Comfort Query

Subjects will be asked to assess the ocular and skin comfort query of the eye of the study eyelid and study eyelid prior to application of the first study drug at baseline (Day 1) and prior to patch removal on Days 8 ± 1 and 15 ± 1 using a subjective 100 mm Visual Analog Scale (VAS) where 0 mm = very comfortable and 100 mm = very uncomfortable. There will be no descriptors for numbers other than 0 mm and 100 mm on the scale and meaning of the extreme ends of the scale. VAS scores will be collected electronically as part of the subject electronic diary.

5.6 Presence of a Chalazion

The presence or complete absence of a chalazion on the study eyelid will be evaluated by the investigator at each study visit at screening/baseline (Day 1), and at 30 minutes to 1 hour after patch removal on Days 8 ± 1 and 15 ± 1 . Absence of a chalazion is determined by the investigator's clinical judgment and may accompany scarring or skin defects resulting from healing of the chalazion. This evaluation should be done by the same investigator throughout the study period as much as possible.

Subjects will also document in their subject electronic diary if the chalazion is still present or not daily from Day 1 through Day 15 ± 1 .

5.7 Size of the Chalazion

The size of the chalazion on the study eyelid will be evaluated by the investigator at each study visit at screening/baseline (Day 1), and at 30 minutes to 1 hour after patch removal on Days 8 ± 1 and 15 ± 1 . The size will be measured [REDACTED]

[REDACTED] The size will not be evaluated on Days 8 ± 1 and 15 ± 1 if the study chalazion is determined to be absent. This evaluation should be done by the same investigator throughout the study period as much as possible.

5.8 Erythema of the Chalazion

The investigator will assess erythema of the chalazion on the study eyelid at each study visit at screening/baseline (Day 1), and at 30 minutes to 1 hour after patch removal on Days 8 ± 1 and 15 ± 1 . The quantitative scale for this assessment is described below (Table 3). This evaluation should be done by the same investigator throughout the study period as much as possible.

Table 3: Erythema of the Study Chalazion

Score	Score Description
0	No signs of erythema
1	Slight erythema
2	Mild erythema
3	Moderate erythema
4	Severe erythema

5.9 Pain Associated with Chalazion Assessment

Subjects will be asked to assess the pain associated with the chalazion using a VAS. The VAS will be specific for pain associated with the chalazion by asking the following questions: “How intense is your pain associated with the chalazion in your eyelid” and “How intense is your pain associated with the chalazion in your eye”. For each question, a 100 mm VAS will be used with no numbers or hash marks. This assessment will be done at screening/baseline (Day 1), and at 30 minutes to 1 hour after patch removal on Days 8 ± 1 and 15 ± 1 . The pain will not be evaluated if the study chalazion is determined to be absent. The VAS scores will be collected electronically as part of the subject electronic diary.

5.10 Appropriateness of Measurements

The ocular safety measurements used in the study (AEs, VA, slit-lamp biomicroscopy, IOP measurement) are generally recognized as reliable, accurate, and relevant in assessing the safety of topical ophthalmic pharmaceutical drugs.

This is the first study to evaluate a transdermal delivery methodology for ophthalmic medication; it is thus considered appropriate to capture the subject’s impressions of ocular and dermal comfort during and after wearing the study drug. For both assessments, the subjects will use a 100 mm VAS, where 0 mm = very comfortable and 100 mm = very uncomfortable, to rate the comfort.

The Draize scale that will be used for scoring dermal response (see Table 2) caused by the study drug, as well as the scale that will be used to evaluate patch adhesion (see Section 5.4), have been widely used by all regulatory authorities for evaluation of skin irritation (4).

The primary endpoints are clinical evaluation of the eyelid and determination of the presence or absence of a chalazion. While slight scarring or distortion of the skin may remain due to the granuloma, the assessment of healing of the chalazion will be based on clinical judgment. Subjects who exhibit a complete resolution of the chalazion based on clinical examination at any time in the study will be considered a CR.

The secondary outcome measures include time to CR of the chalazion as documented by the subject in the patient diary. The size of the study chalazion will also be evaluated and its rationale given that complete resolution may not occur; however, the size of the chalazion may be significantly reduced with treatment. The erythema of the chalazion site itself will also be assessed using a 5-point scale common in ophthalmology for evaluating the redness of the chalazion. In some cases, the chalazion can cause pain either in the eyelid or the eye itself. As such, a pain VAS will be used to ask the subject to assess either the pain in the eyelid caused by the chalazion or the pain in the eye itself that may occur due to pressure on the eye from the chalazion.

5.11 Primary Efficacy Variables

The primary efficacy variables in this trial are the CR of the study chalazion by Day 15 \pm 1. Complete response is defined as the absence of any significant clinical signs of a chalazion, based on clinical judgment by an investigator. Scarring or skin defects resulting from healing of the chalazion are possible and allowed upon CR.

5.12 Secondary Efficacy Variables

[REDACTED]

5.13 Drug Plasma Concentration Measurements

No pharmacokinetic sampling will be taken in this protocol.

6 ADVERSE EVENTS

An AE is any unfavorable and unintended sign, symptom, or disease temporally associated with the use of a study drug or other protocol-imposed intervention, regardless of attribution. An AE may include intercurrent illnesses or injuries that represent an exacerbation (increase in frequency, severity, or specificity) of pre-existing conditions (e.g., worsening of asthma).

The reporting period for AEs (non-serious and serious) starts after the first study drug application on Day 1 and ends at Follow-Up Telephone Contact (Day 22 \pm 3).

The investigator will assess AEs for severity, for relationship to investigational product (IP), and as to whether the event meets one or more of the definitions of a serious adverse event (SAE) (see Section 6.1).

Whenever possible, it is preferable to record a diagnosis as the AE term rather than a series of symptoms relating to a diagnosis. AEs will be graded according to the National Cancer Institute (NCI) Common Terminology Criteria for Adverse Events (CTCAE) v4.0. The investigator will determine the severity of each AE based on NCI CTCAE criteria and will record the grade of the event on the source documents and AE CRF.

NCI CTCAE Grade	Common Term	Description
1	Mild	Mild; asymptomatic or mild symptoms; clinical or diagnostic observations only; intervention not indicated.
2	Moderate	Moderate; minimal, local or noninvasive intervention indicated; limiting age-appropriate instrumental Activities of Daily Living (ADL).
3	Severe	Severe or medically significant but not immediately life-threatening; hospitalization or prolongation of hospitalization indicated; disabling; limiting self-care ADL.
4	Life-Threatening	Life-threatening consequences; urgent intervention indicated.
5	Death	Outcome of AE was death.

***Please note:** severity of an event does not necessarily correlate to the event being defined as a Serious Adverse Event (SAE).

The investigator will determine the relationship of an AE to the IP and will record it on the source documents and AE CRF, using the categories defined below.

Causality Category	Description
Unlikely	A clinical event, including laboratory test abnormality, with a temporal relationship to drug administration which makes a causal relationship improbable, and in which other drugs, chemicals or underlying disease provide plausible explanations. For the purpose of this protocol, the term unlikely will be considered not related to study medication and an “Adverse Event”.
Possible	A clinical event, including laboratory test abnormality, with a reasonable time sequence to administrations of the drug, but which could also be explained by concurrent disease or other drugs or chemicals. Information on drug withdrawal may be lacking or unclear. For the purpose of this protocol an event that has possible relationship to study medication will be defined as a “Suspected Adverse Drug Reaction”.
Probable	A clinical event, including laboratory test abnormality, with a reasonable time sequence to administration of the drug, unlikely to be attributed to concurrent disease or other drugs or chemicals, and which follows a clinically reasonable response on withdrawal. For the purpose of this protocol an event that has probable relationship to study medication will be defined as an “Adverse Drug Reaction”.

In order to classify AEs and diseases, preferred terms will be assigned by the sponsor or its designee to the original terms entered on the CRF, using MedDRA (version 19.1).

An Unexpected AE is defined as an adverse reaction, the nature or severity of which is not consistent with the product information provided in the Investigator’s Brochure.

The medical monitor, in consultation with the investigator, will be responsible for determining without unmasking the subject, whether an AE is clinically significant for the subject or the study overall.

Should a pregnancy occur, it must be reported and recorded on the pregnancy form. Treatment should be stopped at the time when the pregnancy is reported. Pregnancy in itself is not regarded as an AE. The outcome of all pregnancies (spontaneous miscarriage, elective termination, normal birth, or congenital abnormality) must be followed up and documented even if the subject was discontinued from the study.

6.1 Serious Adverse Events

An SAE is defined as any AE that:

- Results in death (i.e., the AE actually causes or leads to death);
- Is life-threatening (i.e., the AE, in the view of the investigator, places the subject at immediate risk of death. It does not include an AE that, had it occurred in a more severe form, might have caused death);
- Requires or prolongs in-patient hospitalization;
- Results in persistent or significant disability or incapacity (i.e., the AE results in substantial disruption of the subject's ability to conduct normal life functions);
- Results in a congenital anomaly or birth defect in a neonate/infant born to a mother exposed to IP prior to conception or during pregnancy;
- Is considered a significant medical event by the investigator based on medical judgment (e.g., may jeopardize the subject or require medical or surgical intervention to prevent 1 of the outcomes listed above).

The reporting period for SAEs will begin after the first study drug application on Day 1 and continue through Day 22 ± 3. Serious AEs reported to the investigator outside of this reporting period will be reported to Senju or the medical monitor, if, in the investigator's judgment, the event has any bearing on the study data. SAEs must be followed by the investigator until resolution, or until the subject is lost to follow-up, even if this extends beyond the study-reporting period. Resolution of an SAE is defined as the return to baseline status or stabilization of the condition with the expectation that it will remain chronic.

Any SAE, whether or not considered a suspected adverse drug reaction, will be reported immediately (within 24 hours of learning of the event) by fax or email using the study-specific SAE Report Form. In addition to the outcome of the SAE, any medication or other therapeutic measures used to treat the event will be recorded on the appropriate CRF page(s). Investigators should not wait to collect additional information that fully documents the event before notifying Senju of an SAE. Senju may be required to report certain SAEs to regulatory authorities within 7 calendar days of being notified about the event; therefore, it is important that Investigators submit additional information requested by Senju as soon as it becomes available.

Reporting of SAEs to the IRB/EC will be done in compliance with the standard operating procedures and policies of the IRB/EC and with applicable regulatory requirements. Adequate documentation must be obtained by Senju showing that the IRB/EC is properly and promptly notified as required.

The SAE form must be either faxed to [contact] or emailed within 24 hours to [contact].

The investigator is encouraged to discuss with the medical monitor any AEs for which the issue of seriousness is unclear or questioned. Contact information for the medical monitor is as follows:

Medical Monitor: [REDACTED]

Cellular: [REDACTED]

Email: [REDACTED]

7 STATISTICAL METHODS AND DETERMINATION OF SAMPLE SIZE

7.1 Statistical and Analytical Plans

All data collected on CRFs will be presented in data listings. The primary and secondary endpoints for this trial will be evaluated using the Intent-to-Treat (ITT) population with the Modified Intent-to-Treat (mITT) performed as a sensitivity analysis. The safety analyses will be carried out using the safety population. Comfort scores (ocular, skin, and the average of both), patch adhesion, and residual drug content will be analyzed using the ITT population (and mITT and Per-Protocol [PP] populations if there are subjects with protocol deviations or incomplete data). In general, the grade for each measure in each eye will be used for analysis of treatment effects unless otherwise specified. All analyses will be conducted in a validated instance of SAS 9.1 or higher.

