3 INVESTIGATIONAL PLAN

3.1 Overall Study Design and Plan

This is a multi-center, double-masked, randomized, placebo-controlled evaluation of the safety and efficacy of SUN-131 1.5% TDS as compared to placebo TDS in subjects with a chalazion. Subjects who may be enrolled will have only one eyelid having a single chalazion with a single visible granuloma, and its size $\leq 36 \text{ mm}^2$ and erythema scale score ≥ 1 .

Subjects meeting all inclusion and exclusion criteria will be centrally randomly assigned to receive one of the following treatments in the affected eyelid:

- SUN-131 1.5% TDS (n = 130)
- Placebo TDS (n = 130)

The randomization will be stratified by age group (<12 years, ≥ 12 years).

Subjects will be trained to apply the placebo TDS during screening. Subjects (or the guardian/caregiver) will apply the study drug on the study eyelid daily for 14 days. At baseline prior to application of the study drug, subjects will be assessed in both eyes for VA, slit-lamp biomicroscopy, IOP measurement, skin and ocular comfort query of the study eyelid and eye of the study eyelid, and skin irritation of study drug application site separate from the chalazion on the study eyelid. The chalazion site itself will also be assessed for erythema, pain related to the

chalazion, and the size of the chalazion by measuring the height and width of the chalazion with a caliper. A photograph of the chalazion at baseline will also be taken prior to first application of the study drug.

On Day 1, the subject may apply the first study drug in the clinic or at home depending on the anticipated schedule for study drug application for the entire treatment period. On Days 8 ± 1 and 15 ± 1 , the study drug should not be replaced with a new study drug in the morning of the visit to ensure the study drug is worn for minimum of 12 hours before removal by the investigator at the site. The subject may wear the study drug over 24 hours on these visit days if necessary. On Day 8 ± 1 , subjects should apply a new study drug after completion of evaluations to ensure the study drug is worn for minimum of 16 hours on that day. The subject can then return to their normal schedule of study drug removal and replacement.

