Subjects meeting all inclusion criteria and none of the exclusion criteria will be enrolled into the study. Training will be conducted on study procedures and on the appropriate method to apply and remove the study drug. Subjects will be centrally randomly assigned in a 1:1 ratio to receive SUN-131 1.5% TDS or placebo TDS applied to the study eyelid affected by the chalazion. The randomization will be stratified by age group (<12 years, ≥12 years). Subjects will receive a 1-week supply of study drug, including backup study drug, and be instructed to wear the study drug daily for a minimum of 16 hours and a maximum of 24 hours, and gently cleanse and wipe the study eyelid and to allow it to dry for approximately 30 minutes before applying a new study drug.

Subjects will continue to apply the study drug each day on the study eyelid for the full treatment period. Subjects will record the time of study drug application, study drug removal, and any unusual events or patch adhesion issues in a daily subject diary, as well as any missed/fall-off/misapplications. Subjects will keep all used and unused study drug in a provided container and return to the sites.

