7.1.6 Analysis of Safety and Other Measures

Safety measures include AEs, ocular examinations and assessments (VA, slit-lamp biomicroscopy, IOP measurement), and skin irritation assessments.

The number and percentage of subjects reporting AEs during the study will be tabulated by MedDRA SOC and by preferred term within each organ. The AE tables will be separately presented by ocular and non-ocular. Ocular AEs will be tabulated by maximum severity and maximum relationship to treatment. For non-ocular AEs, tables will be generated in the same fashion of ocular AE tables, if necessary. System organ classes summary will be listed with eye disorders first, followed by SOCs listed in order of descending frequency for all subjects. Preferred terms will be listed in order of descending frequency within each SOC. Summaries and listings will be provided for subjects reporting SAEs, subjects experiencing AEs related to study medication, and subjects withdrawing due to an AE. The percentages of specific AEs between treatments may be analyzed using Fisher's exact test if they are extremely unbalanced between groups.

Slit-lamp biomicroscopy will be performed at baseline (pre-dose on Day 1) and just after patch removal on Days 8 ± 1 and 15 ± 1 . All biomicroscopy findings will be graded Normal, Abnormal (not clinically significant), or Abnormal (clinically significant) by the investigator. The frequency distribution (number and percentage) of findings in each treatment group at baseline will be tabulated along with the frequency distribution at each time point. The percentages of slit-lamp biomicroscopy findings between treatments may be analyzed by using Pearson's chi-Square test or Fisher's exact test, if necessary, at each time point.

Visual acuity, IOP, ocular comfort score, skin comfort score, and the patch adhesion assessment score will be summarized using descriptive statistics (number of subjects, mean, median, range, and standard deviation) at each time point. The SUN-131 1.5% TDS will be compared to the placebo TDS results at each time point. The changes from baseline (Day 1) will be calculated and the groups compared. A paired t-test will be used to compare the treatment groups at each time point. Additionally, a Wilcoxon signed-rank test may be used for analysis of the skin irritation scores if the distribution of data appeared to be not normally distributed. All statistical testing will be evaluated using a level of significance (α) of 0.05.

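### The each-eye default in Section 7.1 leaves the unit of analysis for visual acuity, IOP and slit-lamp open, and permits treated and untreated eyes to be pooled as independent records

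*Combined protocol and SAP*

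**What the plan says.** Section 7.1 gives the only general rule on eyes: "In general, the grade for each measure in each eye will be used for analysis of treatment effects unless otherwise specified".

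Section 5.2 makes VA, slit-lamp and IOP bilateral: "All ocular safety evaluations will be performed on both subject eyes at baseline", and again after patch removal at the two later visits. Treatment is one-sided. Under Section 3.4.1, subjects are randomised 1:1 to "receive SUN-131 1.5% TDS or placebo TDS applied to the study eyelid affected by the chalazion". Section 3.1 plans 130 subjects per arm.

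On analysis, Section 7.1.6 says of VA, IOP, comfort and adhesion: "The SUN-131 1.5% TDS will be compared to the placebo TDS results at each time point". It then adds: "A paired t-test will be used to compare the treatment groups at each time point". For slit-lamp, testing is optional: "The percentages of slit-lamp biomicroscopy findings between treatments may be analyzed by using" a chi-square or Fisher test. The level is fixed by "All statistical testing will be evaluated using a level of significance (α) of 0.05". None of this identifies the study eye, an eye-by-eye split, a subject-level summary or an adjustment for two eyes from one person.

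Other measures do not have this gap. Comfort, skin irritation, patch adhesion and the chalazion endpoints are defined on the study eye or eyelid (Sections 3.5.3 to 3.5.5 and 5.3 to 5.9). The primary analysis compares proportions of subjects (Section 7.1.5.1).

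**The concern.** The rule defers to anything specified elsewhere, but for the three bilateral measures nothing else is specified, so the default stands. Three analyses fit the text: both eyes pooled, each eye analysed separately, or the study eye alone. They can give different answers, and the choice could be made after the data are seen.

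Pooling would do harm in two ways. Half the records would come from eyes whose lid received no patch, which dilutes a local effect. Two correlated values per subject would also be counted as independent, which makes the standard error too small.

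IOP is where this matters most. The product is a corticosteroid. Section 1 names raised IOP as a risk of steroid eye drops and presents the patch as limiting exposure to the eye. Section 4.1.2 excludes subjects with raised IOP, glaucoma or an earlier steroid-induced rise. The between-arm IOP comparison is the trial's direct check on that claim of low exposure.

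**Working it through.** The documents give no SD, effect size, power or between-eye correlation for these measures, so there is no figure to reproduce. The calculation below shows what follows **if** eyes are pooled. It is for continuous measures (VA, IOP). The same mechanism would act on slit-lamp percentages counted by eye, but that was not computed.

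**Inputs from the documents**
- n = 130 subjects per arm (Section 3.1), hence 260 eyes per arm and 520 in all if pooled.
- Alpha 0.05 (Section 7.1.6). Sidedness is not stated; two-sided is assumed.

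**Assumed inputs**
- Between-eye correlation rho: 0.5 to 0.8, with 0.3 and 0.9 as outer values.
- Effect in the study eye: 0.4 SD, with 0.35 SD as a second value.
- No effect in the fellow eye.
- A two-sample comparison that treats eyes as independent. The plan does not name this test.

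**Step 1. Dilution.** With an effect d in the study eye and none in the other, the pooled difference is (d + 0)/2 = d/2. For d = 0.4 this is 0.2 SD.

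**Step 2. Standard error, in SD units.**
- Calculated as if eyes were independent: sqrt(2/260) = sqrt(1/130) = 0.0877.
- True: sqrt((1+rho)/130). The ratio of true to calculated is sqrt(1+rho).

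**Step 3. Type I error** = 2 × (1 − Phi(1.96/sqrt(1+rho))).

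| rho | SE ratio | Type I error |
|---|---|---|
| 0.3 | 1.14 | 0.086 |
| 0.5 | 1.22 | 0.110 |
| 0.8 | 1.34 | 0.144 |
| 0.9 | 1.38 | 0.155 |

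A simulation of 10,000 trials gave 0.113 at rho 0.5 and 0.146 at rho 0.8. One eye per subject gave 0.051.

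**Step 4. Power at d = 0.4, rho = 0.7.**
- Pooled: true SE = sqrt(1.7/130) = 0.1143. Power = Phi((0.2 − 1.96 × 0.0877)/0.1143) = Phi(0.246), about 0.60.
- Study eye alone: SE = sqrt(2/130) = 0.1240. Power = Phi(0.4/0.1240 − 1.96) = Phi(1.26), about 0.90.

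**Step 5. A second effect size.** The study eye alone has 80% power at sqrt(2/130) × (1.96 + 0.84) = 0.35 SD. At that effect the pooled test has power of about 0.51. With a standard error corrected for the pairing of eyes, power is 0.41 at rho 0.3 and 0.30 at rho 0.9. Correcting the standard error therefore restores the error rate but not the lost effect.

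**Step 6. Eyes analysed separately.** Each comparison has one record per subject. Nothing is diluted in the study-eye comparison, and the standard error is correct for an independent-groups test.

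**The case against.** A reader might infer that the plan does pool both eyes, so that its VA, IOP and slit-lamp comparisons are already diluted and carry wrong standard errors. The documents do not support that. Using each eye's grade can equally mean analysing right and left, or study and fellow eye, one at a time without averaging. Section 7.1.6 also lists the number of subjects among its summary statistics, which leans against 520 records. The lean is weak, because the same sentence covers comfort and adhesion, which have one value per subject.

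The figures above also describe a two-sample test on eyes, whereas Section 7.1.6 names a paired t-test. They are consequences of one permitted reading, not properties of the written plan. This does not rescue the section, however: a paired test does not fit two independent parallel arms even with one eye per subject. In the Phase 1 study (Section 1.1) active and placebo patches were worn on opposite eyes of the same subject, and paired, eye-level analysis would fit there. That the wording was carried over is only an inference.

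Finally, the scope is narrow. These are safety measures, mainly summarised descriptively, with no stated hypothesis or power claim, and the slit-lamp tests are optional. All of this stands and limits the point. It does not supply the missing unit of analysis.

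**Conclusion.** The point holds in conditional form. The default rule, applied to measures taken in both eyes of subjects treated on one eyelid, leaves the unit of analysis undefined and permits pooling. If eyes are pooled as independent, a purely local effect is halved. Type I error is then about 0.11 to 0.14 for rho of 0.5 to 0.8, and power is about 0.60 instead of 0.90 at 0.4 SD and rho 0.7. If eyes are analysed separately, neither consequence follows.

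The correlation and effect sizes are assumed, and the halving requires no effect in the fellow eye. The complete-response analysis and the study-side measures are not affected. The wording should be settled before unmasking, chiefly for the sake of the IOP comparison.

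**What to change.** Replace the sentence in Section 7.1 with:

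> *Treatment comparisons of VA, IOP and slit-lamp findings use one record per subject, the eye of the study eyelid, with an independent-groups comparison that may adjust for the study-eye baseline. The fellow eye is tabulated separately, and eyes are never pooled as independent units.*

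Bring the paired t-test wording in Section 7.1.6 into line with this.

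The change in the fellow eye should not be added as a covariate. It is measured after randomisation, and if the drug acts on both eyes, adjusting for it would remove part of the effect that the safety comparison is meant to show.

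The cost is analysis-plan wording only. Both eyes are already measured at every visit, so no data collection changes.
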